### 7.9 End of Trial

The end of the trial is defined as last patient last 12-month questionnaire.

# 8. TRIAL INTERVENTION

### 8.1 Name and Description of Interventions

Standard local procedures for coiling (or clipping) the aneurysm will be followed. If the patient has more than one aneurysm the neurovascular team will treat the aneurysm that, in their judgement, is most likely to have caused the SAH (this is normally done on the basis of distribution of blood on CT, and aneurysm morphology on angiogram). If such a decision cannot be made, an attempt will be made to treat all the possible responsible aneurysms together.

### 8.2 Known Risks

Standard care for grade 4/5 SAH patients will be provided to all study participants. Initially, this is likely to be in an Intensive Therapy Unit or Neurosciences High Dependency Unit. Outcome in SAH patients is often linked to severity of the initial haemorrhage and degree of neurological disability at the time of presentation.

No additional clinical intervention will be undertaken as part of the trial. The treatment to be undertaken in the majority of cases is endovascular aneurysm coiling. Average risk of serious morbidity and mortality in treatment of ruptured aneurysms with this method is approximately 10%. A small number of patients, not technically suitable for coiling, may have neurosurgical clipping of aneurysm(s). These methods are well–established in the treatment of aneurysms; no new treatment method will be used in this trial.

## 8.3 Assessment of Compliance

After hospital discharge, the GP may be contacted, to establish that the patient is still alive and to obtain information about the patient's clinical condition. If the patient is known to be alive, the study questionnaire will be sent by post with a reply postage paid envelope. Alternatively, patients can complete the questionnaire online via the trial website (www.topsat2.co.uk), if they wish. If no response is received within two weeks, an initial postal reminder will be sent. If no reply is received within a further two weeks, telephone contact will be made with the patient/next of kin (if next of kin gave assent) by the research team or one of the local investigators.

If the patient is unable to complete the questionnaire themselves, a relative or friend can complete it on the patient's behalf.

# 9. SAFETY REPORTING

## 9.1 Standard SAE Definitions

Term	Definition			
Adverse Event (AE)	Any untoward medical occurrence in a participant, including occurrences which are not necessarily caused by or related to the intervention under study.			
Adverse Reaction (AR)	An untoward or unintended response in a participant to which is related to the intervention under study i.e. that a causal relationship between the trial intervention and an AE is at least a reasonable possibility and the relationship cannot be ruled out.			
	All cases judged by either the reporting medically qualified professional or the Sponsor as having a reasonable suspected causal relationship to the trial intervention qualify as adverse reactions.			
Serious Adverse Event (SAE)	
 
A serious adverse event is any untoward medical occurrence that:
 
Results in death
 
Is life-threatening*
 
Requires inpatient hospitalisation or prolongation of existing hospitalisation
 
Results in persistent or significant disability/incapacity
 
Consists of a congenital anomaly or birth defect
 
Other important medical events that jeopardise the participant or require intervention to prevent one of the above consequences
 
* - life-threatening refers to an event in which the participant was at immediate risk of death at the time of the event; it does not refer to an event which hypothetically might have caused death if it were more severe.
 
			
Serious Adverse Reaction (SAR)	An adverse event that is both serious and, in the opinion of the reporting Investigator, believed with reasonable probability to be due to the trial intervention, based upon the information provided.			
Unexpected Serious Adverse Reaction (USAR)	A serious adverse reaction, the nature and severity of which is not consistent with the known information about the intervention under study.			

# 9.2 Recording and Reporting AEs and SAEs for the TOPSAT2 study

All adverse events related to the study intervention (randomisation to either the early treatment arm or treat on improvement arm) should be reported. Depending on the nature of the event, the reporting procedures below should be followed. Any questions concerning adverse event reporting should be directed to the Chief Investigator in the first instance. A flowchart (figure 1) is given in Section 9.8 to aid reporting procedures.

- Adverse events will be collected and recorded in the medical notes and in the eCRF.
- Any serious adverse events will be recorded throughout the duration of the trial until the end of study follow-up (12 months) and tracked until the SAE is resolved.
- Serious adverse events occurring to a subject after the treatment of that subject has ended should be reported to the sponsor if the investigator becomes aware of them.
- The investigator does not need to actively monitor subjects for adverse events once the trial has ended.
- Serious adverse events exclude any pre-planned hospitalisations (e.g. elective surgery) not associated with clinical deterioration.
- Serious adverse events exclude routine treatment or monitoring of the studied indication, not associated with any deterioration in condition.
- Serious adverse events exclude elective or scheduled treatment for pre-existing conditions that did not worsen during the study.

For each SAE the following information will be collected:

- Full details in medical terms and case description
- Event duration (start and end dates, if applicable)
- Action taken
- Outcome
- Seriousness criteria
- Causality in the opinion of the investigator
- Whether the event is considered expected or unexpected.

Any change of condition or other follow-up information should be communicated to the Sponsor/ NCTU as soon as it is available or, at least within 24 hours of the information becoming available. SAE forms should be faxed via the SOHO66 fax-to-email service, which distributes the form as an email to CTU, the UK sponsor and the Chief Investigator. If sites are unable to fax the form, it should be scanned and sent as an encrypted email attachment to [contact]. Events will be followed up until the event has resolved or a final outcome has been reached.

# 9.3 Causality

The assignment of causality should be made by the investigator delegated this task on the site delegation log using the definitions in the table below. All adverse events judged as having a reasonable suspected causal relationship to a study procedure (i.e. definitely, probably or possibly related) are considered to be related adverse events. If any doubt about the causality exists, the local investigator (PI) should inform the Chief Investigator. In the case of discrepant

views on causality between the investigator and others, all parties will discuss the case. In the event that no agreement is made, the REC and other bodies will be informed of both points of view.

Relationship	Description	
Unrelated	There is no evidence of any causal relationship	
Unlikely	There is little evidence to suggest there is a causal relationship (e.g. the event did not occur within a reasonable time after administration of the study procedure). There is another reasonable explanation for the event (e.g. the participant's clinical condition, other concomitant treatment).	
Possible	There is some evidence to suggest a causal relationship (e.g. because the event occurs within a reasonable time after administration of the study procedure). However, the influence of other factors may have contributed to the event (e.g. the participant's clinical condition, other concomitant treatments).	
Probable	There is evidence to suggest a causal relationship and the influence of other factors is unlikely.	
Definitely	There is clear evidence to suggest a causal relationship and other possible contributing factors can be ruled out.	
Not assessable	There is insufficient or incomplete evidence to make a clinical judgement of the causal relationship.	

## Expected adverse reactions:

Most adverse events that occur in this study, whether they are serious or not, will be expected due to the interventions and study procedures. Expected AEs are summarised in the following table.

Frequencies are defined as common ( $\geq$  1/100 to < 1/10); uncommon ( $\geq$  1/1,000 to < 1/100); rare ( $\geq$ 1/10,000 to <1/1,000); very rare (<1/10,000); not known (cannot be estimated from the available data).

## AEs related to acute sub-arachnoid haemorrhage:

- Neurological
- Systemic

Condition	Common	Uncommon	Very Rare
Neurological	Death, impaired cerebrospinal fluid drainage-related, vasospasm-related, re- bleed, brain swelling/oedema, neuropsychological and cognitive, stroke, epilepsy (and sequelae); depression	Additional aneurysm-related, visual, cranial nerve palsy	visual loss

Systemic	Cardiorespiratory; renal; infections	Myocardial	
Systemic	(including pneumonia, urinary tract	infarction	
	infection , cellulitis, ventriculitis and		
	hospital acquired infections;); complications		
	of prolonged immobility including falls (and		
	sequelae),		
	deep vein thrombosis, pulmonary embolism		
	, pressure sores, spasticity, pain; fluid		
	balance and electrolytic disturbances		
	including syndrome of inappropriate		
	antidiuretic hormone secretion and		
	cerebral salt wasting; frailty		

#### AEs related to aneurysm treatment:

- Coiling
- Clipping

Procedure	Common	Uncommon	Very Rare
Coiling	Rupture; dissection/vessel perforation; anaesthetic-related; arterial puncture site- related; adjunctive drug-related (such as Heparin, Aspirin, Nimodipine);stroke; coil prolapse/parent vessel occlusion; vasospasm	Epilepsy; myocardial infarction; ; contrast media- related; radiation-related death	; visual loss
Clipping	Stroke; infection; anaesthetic; drain insertion- related; epilepsy; vasospasm	Brain retraction related; re- bleed death; myocardial infarction	

# 9.4 Recording and Reporting Unexpected Serious Adverse Reactions

All Unexpected Serious Adverse Reactions (USARs) occurring in the 30 days post-intervention must be reported to the NHS REC. The Sponsor will perform this reporting. A separate procedure for non-UK sites is given in the non-UK protocol.

The assessment of expectedness will be performed by the Sponsor/CI against the known information for the trial.

USARs must be reported no later than 15 calendar days after the Sponsor has first knowledge of the event. Any relevant follow-up information should be sought and reported as soon as possible after the initial report.

As soon as a site suspects that a SAR may be a USAR they must contact the CI, sponsor representative and the Trial Manager immediately. The reporting timeframe starts at day 0 when the Sponsor is in receipt of a minimum set of information:

- Sponsor trial reference and trial name (sponsor reference)
- Patient trial number and date of birth
- Name of intervention
- Date of notification of the event
- Medical description of the event
- Date and time of onset of the event (including event end date if applicable)
- Causality assessment
- Seriousness of the event, particularly if life threatening or fatal
- An identifiable reporter (e.g. Principal Investigator)

This information can be reported by telephone, email or fax. The site is expected to fully cooperate with the Sponsor so that a full and detailed report can be submitted to the NHS REC within the required timelines.

PIs will be informed of all USARs by the Sponsor.

## 9.5 Responsibilities

#### Principal Investigator

- Checking for AEs and ARs when participants attend for treatment or follow-up
- Using medical judgement in assigning seriousness and causality and providing an opinion on expectedness of events
- Ensuring that all SAEs and SARs, including USARs, are recorded and reported to the Sponsor within 24 hours of becoming aware of the event and providing further follow-up information as soon as available
- Ensuring that AEs and ARs are recorded and reported to the Sponsor in line with the requirements of the protocol.

#### **Chief Investigator**

- Clinical oversight of the safety of trial participants, including an ongoing review of the risk/benefit.
- Using medical judgement in assigning seriousness, causality and expectedness of SAEs where it has not been possible to obtain local medical assessment
- Using medical judgement in assigning expectedness to SARs
- Immediate review of all USARs
- Review of specific SAEs and SARs in accordance with the trial risk assessment and protocol.

#### Sponsor

- Assessment of expectedness of any USARs
- Expedited reporting of USARs to the REC within required timelines
- Notification of all investigator sites of any USAR that occurs.

#### TSC/DMC

[figure not shown]
• Review of safety data collected to date to identify any trends

# 9.6 Notification of Deaths

Death is a common outcome in grade 4-5 aSAH, therefore REC will not be notified of these events unless due to serious, related and unexpected AE (USAR). All deaths occurring during the study that the site staff become aware of should be reported as SAEs.

# 9.7 Reporting Urgent Safety Measures

An Urgent Safety Measure (USM) is an action that the Sponsor or an Investigator may take in order to protect the subjects of a trial against any immediate hazard to their health or safety. Upon implementation of an USM by an Investigator, the CI and NCTU must be notified immediately and details of the USM given. The CI or NCTU must inform the Sponsor immediately. The Sponsor must inform the NHS REC within three days of the USM taking place in accordance with NCTU standard operating procedures.

# 9.8 Safety Reporting Diagram

# Contact details for reporting SAEs and USARs

Please fax SAE form(s) via SOHO66 fax-to-email service on [name] Or If for any reason sites are unable to fax the SAE form, they must scan and email the form securely encrypted to [contact].

# **10. STATISTICAL CONSIDERATIONS**

## **10.1** Analysis Population

The aim is to collect outcome on all patients randomised to the study who do not withdraw consent.

## **10.2 Statistical Analyses**

#### 10.2.1 Analysis of the Primary Outcome Measure

Outcome analysis will take place once all data has been collected, cleaned and the database locked. Trial analysis will be on a modified intention-to-treat basis. Where patients are lost to follow-up they will be removed from the primary outcome analysis; however a sensitivity analysis will be performed to assess the effect of missing data. The primary outcome will be a comparison of the mRS, treated as an ordinal scale, at 12 months (including death coded as 6) under the two treatment strategy arms using a proportional odds model. A sensitivity analysis will be undertaken of the proportional odds model (of primary outcome), adjusting for the minimisation criteria (WFNS grade, age band, hydrocephalus requiring drainage, and whether the patient is randomised within the UK or not). Per protocol analysis will also be performed. If a subject withdraws, all data collected up until that point will be used in trial analysis, unless he/she specifically refuses. In that case, if the trial is still recruiting an additional subject will be randomised.

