### 7.4 Randomisation

Randomisation will be carried out by the research team at sites through the use of a web-based system accessed via the trial website (www.topsat2.co.uk), and hosted by the Health Services Research Unit, University of Aberdeen. This service is available 24/7. Further information is

available in the randomisation SOP. The randomisation will utilise a minimisation algorithm with 80% chance of being allocated to the minimisation group to reduce differences in two arms with respect to the following (with 20% following a totally random allocation):

- Grade 4 and 5 (so distributed equally in the two arms)
- Participant age at the time of randomisation (age bands 18-50, 51-65 and 66-80)
- Presence of clinically significant hydrocephalus requiring CSF drainage procedure (yes/no)
- UK/non-UK centre.

The randomisation service will automatically confirm randomisation details to the person carrying out the randomisation, and NCTU, by email.

If the patient is randomised to the early treatment arm, the result of randomisation will be communicated to the neurovascular team who will treat the aneurysm. They will decide on the most appropriate treatment strategy but, as per the RCT evidence base, if the aneurysm is technically amenable to coiling, coiling will be the initial therapeutic option. The usual institutional surgical consent form for the procedure will then be completed and the aneurysm must be treated within 24 hours of randomisation, and 72 hours of ictal bleed that led to hospital admission.

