## 10.2.2 Analysis of Secondary Outcome Measures

Secondary outcomes of dichotomised mRS (0-3 v 4-6; 0-2 v 3-6) at discharge, six and 12 months, mortality rate at 30 days, six and 12 months, re-bleeding rate and treatment-related complication rate between the arms will be compared using a chi-squared test; odds ratios will be reported. MRS at discharge and six months will be compared using a proportional odds model. These will further explain differences between the two treatment policies. Survival, time to discharge and length of ITU/HDU stay will be compared between arms using survival plots, and the log rank test will be reported. The latter two highlight differences between the two treatment arms in the NHS costs of the two treatments.

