## **10.3** Statistical Size Calculations

The outcome measure in TOPSAT2 is based on the mRS. This is a seven-point scale with values 0 to 5 representing increasing disability and a value of 6 representing death. In the past it was common to dichotomise such a scale for outcome analysis, resulting in a loss of information as not all patients contribute to the detection of a treatment effect. The Optimising Analysis of Stroke Trials (OAST) Collaboration and other authors have recently shown the benefit of ordinal analysis in the field of stroke . Using an ordinal analysis achieves substantially greater statistical power to detect a treatment effect with equal sample size. The sample size calculation is therefore based on a proportional odds regression ordinal analysis of the mRS.

The best available literature, a non-randomised study, was used to provide the expected distribution of mRS after grades 4 and 5 aSAH. Detecting a difference in clinical outcome (i.e. favouring one treatment strategy over the other) by an odds ratio of >1.5 would be compelling evidence to rapidly change to a uniform practice, as would a number needed to treat (NNT) of <10. Expected mRS distribution data (0, no symptoms 17%; 1, minor symptoms 10%; 2, some restriction in lifestyle 6%; 3, significant restriction in lifestyle 19%; 4, partially dependent 11%; 5, fully dependent 10%; 6, dead 27%) was entered into the "Sample size for ordered categories" routine of the Compare2 program in WinPepi version 11.43 July 2014 and using two-sided significance of 5%, power of 80%, and 1:1 ratio of sample size, the sample sizes needed for different odds ratios (where the odds ratio is assumed to be the same at all cutting points) were examined.

With 167 participants in each arm, a proportional odds model ordinal analysis of mRS, gives a cumulative Odds Ratio (OR) in favour of better mRS in one treatment arm of 1.7 at 5% significance level and 80% power. A margin is built in to allow for losses to follow-up and crossovers meaning a total sample size of 346 will be recruited (173 per arm). Loss to follow-up of <2% is based on data from multiple UK-based aneurysm coiling trials.

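### The primary proportional odds model ignores the four factors used for minimisation, so the test is conservative and some power is forgone

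*Protocol*

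**What the plan says.** Protocol Section 7.4: "The randomisation will utilise a minimisation algorithm with 80% chance of being allocated to the minimisation group". The factors are WFNS grade (4 or 5), age in three bands, hydrocephalus needing a drainage procedure, and UK or non-UK centre.

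Protocol Section 10.2.1 compares 12-month mRS between the two arms with a proportional odds model and names no covariates for it. It continues: "A sensitivity analysis will be undertaken of the proportional odds model (of primary outcome), adjusting for the minimisation criteria", listing the same four factors. If the primary model already held them, this sensitivity analysis would repeat it, so the primary model is unadjusted.

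Protocol Section 10.2.2 handles the binary secondary outcomes in the same way. Dichotomised mRS and mortality are on the list, which ends: "re-bleeding rate and treatment-related complication rate between the arms will be compared using a chi-squared test".

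Protocol Section 10.3 sizes the trial without covariates, "using two-sided significance of 5%, power of 80%, and 1:1 ratio of sample size", from one pooled mRS distribution.

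**The concern.** Minimisation forces the arms to resemble each other on the chosen factors. If those factors predict outcome, the treatment estimate varies less from trial to trial than under simple randomisation. The standard error of an unadjusted model takes no account of this and is too large. The test then rejects less often than its nominal level, and intervals cover more often than 95%.

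The protocol shows that at least one factor is prognostic. Section 1 (NCEPOD report) gives good outcome at discharge in 38% of grade 4 and 15% of grade 5 patients, and Section 10.3 refers to appreciable differences between the grades. At stake is power that the design has already paid for, in a trial with little slack: 346 patients against a calculated 334.

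**Working it through.** **The plan's own figure.** "With 167 participants in each arm, a proportional odds model ordinal analysis of mRS, gives a cumulative Odds Ratio (OR) in favour of better mRS" of 1.7. Whitehead's formula for n per arm is 6(z₀.₉₇₅ + z₀.₈₀)² / [(ln OR)² (1 − Σp̄³)], where p̄ is the mean of the two arms' category probabilities.

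- Leaving out the tie term (1 − Σp̄³): 6 × (1.960 + 0.842)² / 0.5306² = 167.3, which matches 167.
- With the stated distribution (17, 10, 6, 19, 11, 10, 27%) and OR 1.7, Σp̄³ = 0.0316. Then n = 167.3 / 0.9684 = 172.7.
- Power at 167 per arm with the tie term: √(167 × 0.2816 × 0.9684 / 6) − 1.960 = 0.795, or 78.7%.

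The stated 80% for an unadjusted two-arm comparison is thus reproduced to within 2 points.

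**Prognostic strength of grade.** OR = (0.38/0.62) / (0.15/0.85) = 3.47. The same NCEPOD section reports about equal numbers in the two grades.

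**Analytic check on type I error.** With a 50:50 split, grade adds (ln 3.47 / 2)² = 0.387 to a logistic latent variance of π²/3 = 3.29. Its share is 0.387 / 3.677 = 10.5%. If minimisation removes this share from the comparison, the effective critical value is 1.96 / √0.895 = 2.07, a true two-sided level of about 3.8%.

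**Simulation.** Set-up: 80/20 minimisation on all four factors, the stated mRS distribution as the control margin, and Wald tests from proportional odds fits with and without the four factors, with 4,000 to 16,000 trials per cell. Assumed because the protocol does not give them: equal age bands, 40% hydrocephalus, and every prognostic effect except that of grade.

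Grade alone prognostic, OR 3.47:

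| N | Reading of OR 1.7 | Unadjusted power | Adjusted power | Difference (points) |
|---|---|---|---|---|
| 334 | within stratum | 73.8% | 78.4% | 4.5 |
| 346 | within stratum | 74.9% | 80.1% | 5.2 |
| 334 | marginal | 79.4% | 83.7% | 4.3 |
| 346 | marginal | 81.2% | 85.5% | 4.3 |

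Type I error at N=334 is 3.7% unadjusted and 5.1% adjusted. A separate simulation at N=346, within-stratum OR 1.7, gives 75.4% v 79.5% power and 3.4% v 4.7% type I error.

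Other assumed effects, N=334, within-stratum OR 1.7 (age OR is per band):

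| Assumed prognostic ORs | Unadjusted power | Adjusted power | Difference (points) | Unadjusted type I error |
|---|---|---|---|---|
| none | 79.4% | 79.7% | none beyond noise | 5.0% |
| grade 1.5, age 1.2, hydrocephalus 1.2 | 77.8% | 79.5% | 1.7 | 4.7% |
| grade 2, age 1.5, hydrocephalus 1.5 | 75.1% | 78.5% | 3.4 | 4.2% |
| grade 3.47, age 1.5, hydrocephalus 1.5 | 71.3% | 78.0% | 6.6 | 3.3% |
| grade 3.47, age 2, hydrocephalus 2, UK 1.3 | 67.8% | 77.3% | 9.5 | 2.7% |

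With grade alone at OR 2 the gain is about 1.5 points.

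**Where the gain comes from.** With grade at 3.47 the mean model standard error of the log OR is 0.191 unadjusted and 0.193 adjusted, so adjustment does not shorten the interval. The estimates differ: about 1.63 unadjusted against 1.7 adjusted. The ratio of log OR to standard error is ln 1.63 / 0.191 = 2.56 against ln 1.7 / 0.193 = 2.75.

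**The case against.** The strongest reply is that nothing here is invalid. The unadjusted test errs on the safe side and the adjusted model is already prespecified with the right covariates. The sample size was also derived without covariates from a single pooled distribution, so 1.7 is most naturally a marginal odds ratio. On that reading the planned test has 79.4% power at 334, essentially what was promised. This stands. A reader might infer that the trial is underpowered because of its analysis. The protocol does not support that, since the lower figures (73.8%, 74.9%) apply only if 1.7 is meant within strata.

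Three further inferences also fail:

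- *That the unadjusted odds ratio is biased.* The move from 1.7 to about 1.63 is non-collapsibility. The two models estimate different quantities, one marginal and one conditional.
- *That adjustment would give narrower intervals.* The standard errors above show that it would not on the log-OR scale. The fault is over-coverage.
- *That every secondary outcome should carry all four factors.* Sections 2.1 and 8.2 put the procedural risk of coiling between 3-5% and about 10%. Taken as complication rates in all 346 patients, these give at most about 10 to 35 events (346 × 0.03 to 346 × 0.10). Treatment plus five covariate terms makes six coefficients, so about 2 to 6 events each, which could be unstable.

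The size is also uncertain. The grade figures are outcomes at discharge in a national audit, not 12-month mRS under the eligibility criteria of Section 6. The protocol gives no effect for age or hydrocephalus and does not show that UK/non-UK is prognostic.

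What the reply does not answer is why a trial that balances on these factors should leave them out of its main test. On either reading of 1.7, adjustment adds about 4 points or more when grade has the protocol's own effect.

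**Conclusion.** The point holds as a worthwhile improvement to a valid but inefficient primary analysis. If grade has an odds ratio of 3.47, the unadjusted test runs at about 3.4-3.7% instead of 5%, its intervals over-cover, and about 4-5 points of power are forgone. Across the assumed range of prognostic effects the forgone power is roughly 2 to 10 points, and it is nil if no factor is prognostic. The direction is secure so long as any minimisation factor predicts outcome. The size rests on the discharge figures carrying over to 12-month mRS and on the simulation assumptions listed. It is not shown that the trial misses its stated 80%.

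This rests on the protocol alone. A statistical analysis plan may exist, but the protocol itself fixes which model is primary.

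**What to change.** Before unblinding, exchange the two models in Section 10.2.1. The proportional odds model adjusted for WFNS grade, age band, hydrocephalus needing drainage and UK/non-UK, with values as entered at randomisation, becomes primary. The unadjusted model becomes the sensitivity analysis. State that the reported odds ratio is conditional on these factors.

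In Section 10.2.2, use logistic models with the same covariates for the commoner binary outcomes (dichotomised mRS and mortality). Keep unadjusted or reduced-covariate analyses for sparse outcomes such as re-bleeding and treatment-related complications.

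The cost is a change of wording in the protocol and analysis plan. All four covariates are recorded to run the randomisation and the sample size need not change. It also settles in advance which result governs if the two models fall on opposite sides of p = 0.05.
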